### **Research question:**

What is/are the effect(s) of scapular muscle strengthening compared to PNF exercise on isometric scapular muscle strength, scapular muscles ratio and scapular asymmetry in patients with shoulder impingent syndrome.

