### **Hypotheses of the study:**

1. There will be no significant difference between scapular muscle strengthening and PNF exercise on improving muscle strength of upper trapezius in patients with shoulder impingement syndrome.

2. There will be no significant difference between scapular muscle strengthening and PNF exercise on improving muscle strength of middle trapezius in patients with shoulder impingement syndrome.
3. There will be no significant difference between scapular muscle strengthening and PNF exercise on improving muscle strength of lower trapezius in patients with shoulder impingement syndrome.
4. There will be no significant difference between scapular muscle strengthening and PNF exercise on improving muscle strength of serratus anterior in patients with shoulder impingement syndrome.
5. There will be no significant difference between scapular muscle strengthening and PNF exercise on muscle ratio of upper trapezius/lower trapezius muscles in patients with shoulder impingement syndrome.
6. There will be no significant difference between scapular muscle strengthening and PNF exercise on muscle ratio of upper trapezius/middle trapezius muscles in patients with shoulder impingement syndrome.
7. There will be no significant difference between scapular muscle strengthening and PNF exercise on muscle ratio of upper trapezius/serratus anterior muscles in patients with shoulder impingement syndrome.
8. There will be no significant difference between scapular muscle strengthening and PNF exercise on scapular symmetry at 0° abduction in patients with shoulder impingement syndrome.
9. There will be no significant difference between scapular muscle strengthening and motor control exercise on scapular symmetry at 45° abduction in patients with shoulder impingement syndrome.
10. There will be no significant difference between Scapular muscle strengthening and motor control exercise on scapular symmetry at 90° abduction in patients with shoulder impingement syndrome.

11. There will be no significant difference between scapular muscle strengthening and PNF exercise on improving pain in patients with shoulder impingement syndrome.
12. There will be no significant difference between scapular muscle strengthening and PNF exercise on improving function in patients with shoulder impingement syndrome.

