## Sample size calculation:

In order to detect an effect size of Cohen's  $d = 0.80$  with 80% power ( $\alpha = 0.05$ ), G\*power software (version 3.1.9.7; Franz Faul, Universitat Kiel, Germany) suggests we will need 64 participants, however, we will aim to recruit 66 subjects to have equal groups representation (22 per group) using analysis of variance (ANOVA) test as shown in the (figure 7).

[figure not shown]

Figure 1 ample size calculation

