## Isometric strength imbalance of shoulder girdle muscles:

Isometric strength imbalance of shoulder girdle will be examined bilaterally. Subject will perform four scapular muscle tests (SA, UT, MR and LR). Then agonist and antagonist ratio of UT/SA, and MR/LR will be

[figure not shown]

calculated. Hand held dynamometer (HHD) will be used to record the amount of maximum muscle force applied by the subject during the muscle test.

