## **2. Isometric strength imbalance of shoulder girdle muscles**

Isometric strength imbalance of shoulder girdle will be examined bilaterally. Based on the muscle test results from the previous measurement, The ratio of UT/SA and MR/LR will be calculated.

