**Figure 20 SCAPULAR ANTERIOR DEPRESSION**

## **Statistical analysis**

- Data will be analyzed using the statistical package for social science (SPSS) program, version 27 (SPSS Inc, Chicago, IL, USA).
- Descriptive statistics will be used to summarize the data. Data will be reported as mean  $\pm$  SD for quantitative variables and frequency distribution (%) for categorical variables.
- The normality of data will be checked using Shapiro–Wilk test.
- Levene’s test will be used to check the homogeneity between groups.
- Two-way Multiple Analysis of Variance (MANOVA) will be conducted to compare the mean values of the measured variables of the three groups.
- The level of significance for all statistical tests will be set at  $\alpha = 0.05$ .

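### Twelve unranked hypotheses with no primary outcome or designated primary contrast, a blanket 0.05, and a sample size that rests on a three-group omnibus test

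*Protocol*

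**What the plan says.** All references are to the protocol.

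- **Hypotheses of the study** lists 12 null hypotheses: four muscle strengths, three muscle ratios, scapular symmetry in three arm positions, pain and function. A typical one reads "There will be no significant difference between scapular muscle strengthening and PNF exercise on improving function in patients with shoulder impingement syndrome". Ten name strengthening versus PNF. Hypotheses 9 and 10 name a different comparator: "There will be no significant difference between scapular muscle strengthening and motor control exercise on scapular symmetry". None involves the untreated arm, and none is marked as primary.
- **Purpose of the study** lists five outcome domains side by side. **Research question** lists three, "on isometric scapular muscle strength, scapular muscles ratio and scapular asymmetry in patients with shoulder impingent syndrome", leaving out pain and function.
- **Sample size calculation** asks for d = 0.80, 80% power and α = 0.05, arrives at 64, and continues: "we will aim to recruit 66 subjects to have equal groups representation (22 per group) using analysis of variance (ANOVA) test". It names no outcome and no pair of groups.
- **Statistical analysis** plans a two-way MANOVA comparing the three groups. It then says "The level of significance for all statistical tests will be set at" 0.05.
- On the ratios, hypothesis 5 is "on muscle ratio of upper trapezius/lower trapezius muscles in patients with shoulder impingement syndrome", and hypotheses 6 and 7 concern UT/MT and UT/SA. The assessment procedure says "Based on the muscle test results from the previous measurement, The ratio of UT/SA and MR/LR will be calculated", and the instrumentation section gives the same two ratios ("Then agonist and antagonist ratio of UT/SA, and MR/LR will be").

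**The concern.** The hypotheses ask 12 separate questions, nearly all about one pair of arms. The named analysis asks one joint question about three arms. A significant MANOVA says that some arm differs on some combination of outcomes. It does not say whether strengthening differs from PNF, or on what. To reach the stated hypotheses, someone must run outcome-by-outcome pairwise tests. The only rule the protocol gives for those is 0.05 throughout.

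With no outcome ranked first, either exercise could be reported as better on whichever outcome crosses 0.05. The 80% power cannot be checked against any result, because it belongs to no named outcome and to a test other than the one the hypotheses call for.

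**Working it through.** **Inputs.** From the protocol: d = 0.80, α = 0.05 (two-sided assumed), 80% power, N = 64 raised to 66, 22 per arm, three arms, 12 hypotheses. The protocol gives no SDs or correlations, so those below are assumptions and are varied.

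**1. The stated 64.** Take the omnibus one-way ANOVA with three groups and f = d/2 = 0.40. The noncentrality is N·f², with 2 and N − 3 degrees of freedom.
- N = 63: 63 × 0.16 = 10.08, power 79.8%
- N = 64: 64 × 0.16 = 10.24, power 80.5%
- N = 66: 66 × 0.16 = 10.56, power 81.8%

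So 64 reproduces exactly, as an omnibus test.

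**2. What f = 0.40 implies with three groups.** The conversion f = d/2 is the two-group one. If 0.80 SD is the largest pairwise difference among three equal groups, then:
- means 0, 0.4, 0.8: f = 0.80/√6 = 0.327, power at N = 66 is 63.6%
- means 0, 0, 0.8: f = 0.80·√2/3 = 0.377, power at N = 66 is 76.8%

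The second pattern gives the largest f possible for that range. An f of 0.40 therefore needs a largest pairwise difference of at least 0.40 × 3/√2 = 0.85 SD.

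**3. Power for strengthening versus PNF.** The noncentrality is d·√(n/2) = 0.80 × √11 = 2.653.
- Two-sample t, 42 df (critical value 2.018): 73.6%
- Error pooled over three arms, 63 df (critical value 1.998): 74.3%
- d giving 80% at 22 per arm: 0.865 (42 df) or 0.858 (63 df)
- n for 80% at d = 0.80: 25 per arm gives 79.1%, 26 gives 80.7%, so 3 × 26 = 78 in total
- At 0.05/12 (Bonferroni over all 12), 22 per arm: about 37%

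Here d is on the scale actually analysed. If d = 0.80 is instead in raw SD units, the power depends on the pre–post correlation r. It follows from dividing d by √(2(1 − r)) for change scores or √(1 − r²) for baseline adjustment:

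| r | Change score | Baseline-adjusted |
|---|---|---|
| 0.3 | 59% | 78% |
| 0.5 | 74% | 85% |
| 0.6 | 83% | 90% |
| 0.7 | 92% | 95% |

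**4. Chance of at least one false strengthening-versus-PNF difference, tests run separately at 0.05.** The ceiling under independence is 1 − 0.95¹² = 46.0%. It is not attained, because the ratios are built from the same strength readings. Simulation with 22 per arm, no true difference, and ratios computed from lognormal strengths (log-SD 0.15–0.35), 20,000 runs per setting:

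| Assumed correlation | Chance |
|---|---|
| None beyond the ratios | 40–41% |
| 0.5 strengths; 0.7 positions and pain/function | 37–38% |
| 0.7; 0.8 | 35–36% |
| 0.9 within domains | 32–33% |
| Equal 0.7 across all 12 | 23% |

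The first four rows set the correlation between domains to zero. With only the two ratios of the assessment section (MR/LR read as MT/LT, an assumption), the first four rows become 39–40%, 36%, 33–34% and 30–31%. An equal 0.8 across all 12 outcomes, more extreme than seems plausible, would give 19%.

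**5. The MANOVA used as a gate (not stated in the protocol).**
- All three arms equal: about 1–4%.
- Untreated arm 0.8 SD worse on pain and function only: 15–29%.
- Untreated arm 0.8 SD worse on strengths, positions, pain and function: 32–41% with no correlation between domains. With correlation between domains added, 31–37% at weak to moderate settings, falling to 11% at the strongest.

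In the last two cases the untreated arm opens the gate while strengthening and PNF remain equal.

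**The case against.** The strongest case against is that the protocol plans a MANOVA and no separate pairwise tests, so the error rates describe an analysis nobody has committed to. Follow-up contrasts and multiplicity rules commonly sit in a statistical analysis plan, which is not shown. This stands: the missing multiplicity rule is not the point, and the error rate must be stated conditionally. It does not remove the choice of primary outcome, or the outcome and contrast behind the sample size, which belong in the protocol. The blanket 0.05 is also stated text.

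A reader might infer several stronger things that the document does not support.

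- **That the trial has a 40% or 46% false-positive rate.** The protocol does not lay down separate tests, and 46% holds only under full independence.
- **That the sample size is miscalculated.** The figure of 64 is right for the test it is tied to, and the missing figure in that section may show the number of groups and f.
- **That the trial is underpowered.** Outcomes are measured before and after treatment. With d in raw SD units and baseline adjustment, power could exceed 80%; with change scores and a low correlation it could fall below 74%.
- **That no contrast is named at all.** Ten hypotheses name strengthening versus PNF. What is missing is its designation as primary and a sample size and analysis aimed at it.

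The ratio mismatch and the comparator in hypotheses 9 and 10 are wording inconsistencies and cause neither the error rate nor the power. All four strengths are measured, so UT/LT, UT/MT and UT/SA can be computed.

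**Conclusion.** The point holds as a design gap: 12 unranked hypotheses, no primary outcome, no designated primary contrast, a sample size attached to neither, and a named analysis that cannot answer the hypotheses as worded.

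Its size is conditional. If the hypotheses are tested separately at 0.05, the chance of at least one false strengthening-versus-PNF difference is roughly 23–41%, depending on assumed correlations. A MANOVA gate would hold it to about 1–4% only if all three arms are equal, and to roughly 11–41% if the untreated arm differs by an assumed 0.8 SD. Power for strengthening versus PNF at d = 0.80 on the analysed scale is about 74%, with no dropout and no gain from baseline data. The omnibus test has 64–77% if 0.80 is the largest pairwise difference.

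Confidence is high in the textual gap and in the power arithmetic. It is lower in the error-rate range, which rests on correlations the protocol does not give. The matter should be corrected before analysis.

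**What to change.** 1. Name one primary outcome, chosen by the investigators from those already collected, and strengthening versus PNF as the primary contrast at two-sided 0.05.
2. Make the other hypotheses secondary: either Holm-adjusted, or reported as strengthening-minus-PNF estimates with 95% confidence intervals and no significance claims. Reword the blanket 0.05 sentence to match.
3. Keep 66 patients and restate the power for the primary contrast: about 74% at d = 0.80, or 80% at d of about 0.86, on the analysed scale. State any assumed gain from baseline adjustment. Say that 64 rests on the three-group omnibus ANOVA with f = 0.40.
4. Separately, reconcile the ratios in hypotheses 5–7 with those in the instrumentation and assessment sections, including what MR and LR denote. Reconcile the comparator in hypotheses 9 and 10 with the three arms under Subjects.

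**Cost.** Protocol wording only: no extra patients or measurements. The downsides are fewer secondary significance claims and a less favourable stated power. Insisting on 80% at d = 0.80 for this contrast without baseline adjustment would need 26 per arm, 78 in all. One primary test is preferable to adjusting all 12, which would cut power at d = 0.80 to about 37% under Bonferroni.

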## Appendix II. Shoulder and pain disability index

Patient Name \_\_\_\_\_ Date \_\_\_\_\_

### Shoulder Pain & Disability Index (SPADI)

Pain Scale: How severe is your pain?

0 \_\_\_\_\_ 10  
 No Pain Worst Pain Imaginable

For each question below, circle the number that best describes your pain based on the scale above

At its worst?	0 1 2 3 4 5 6 7 8 9 10
When lying on the involved side?	0 1 2 3 4 5 6 7 8 9 10
Reaching for something on a high shelf?	0 1 2 3 4 5 6 7 8 9 10
Touching the back of your neck?	0 1 2 3 4 5 6 7 8 9 10
Pushing with the involved arm?	0 1 2 3 4 5 6 7 8 9 10

Disability Scale: How much difficulty do you have?

0 \_\_\_\_\_ 10  
 No Difficulty Unable to Perform

For each question below, circle the number that best describes your difficulty based on the scale above

Washing your hair?	0 1 2 3 4 5 6 7 8 9 10
Washing your back?	0 1 2 3 4 5 6 7 8 9 10
Putting on an undershirt or pullover sweater?	0 1 2 3 4 5 6 7 8 9 10
Putting on a shirt that buttons down the front?	0 1 2 3 4 5 6 7 8 9 10
Putting on your pants?	0 1 2 3 4 5 6 7 8 9 10
Placing an object on a high shelf?	0 1 2 3 4 5 6 7 8 9 10
Carrying a heavy object of 10 pounds?	0 1 2 3 4 5 6 7 8 9 10
Removing something from your back pocket?	0 1 2 3 4 5 6 7 8 9 10
Pain Scale Score: ____ /50 x 100 = ____ % Disability Scale Score: ____ /80 x 100 = ____ %	TOTAL SCORE: ____ /130 x 100 = ____ %

Scoring: Summate the scores and divide by the number of scores possible. If an item is deemed not applicable, no score is calculated. Multiply total score by 100. The higher the score, the greater the impairment.

